6.9 Treatment of Nivolumab- or Ipilimumab-Related Infusion Reactions

Nivolumab- or ipilimumab-related infusion or hypersensitivity reactions are rare. However, when such reactions occur, symptoms/signs may include fever, chills, rigors, headache, rash, urticaria, angioedema, pruritis, arthralgias, hypo- or hypertension, bronchospasm, back pain, or other symptoms.

All grade 3 or 4 infusion reactions should be reported as an SAE if criteria are met. Infusion reactions should be graded according to NCI Common Terminology Criteria for Adverse Events (CTCAE) version 5.0 guidelines.

Treatment recommendations are provided below and may be modified based on local treatment standards and guidelines as medically appropriate:

6.9.1 Grade 1 symptoms: Mild reaction, infusion interruption and/or intervention not indicated.

Infusion rate may be slowed or interrupted and restarted at 50% of the original infusion rate when symptoms resolve; if no further complications ensue after 30 minutes, the rate may be increased to 100% of the original infusion rate. Monitor the patient closely.

The following prophylactic medications are recommended for future infusions:

- Diphenhydramine 50 mg (or equivalent) and/or
- Paracetamol 325-1000 mg (acetaminophen) at least 30 minutes before additional nivolumab administrations

6.9.2 Grade 2 symptoms: Moderate reaction that requires therapy or infusion interruption but responds promptly to symptomatic treatment (e.g., antihistamines, non-steroidal anti-inflammatory drugs, narcotics, corticosteroids, bronchodilators, IV fluids).

Stop the nivolumab infusion, begin an IV infusion of normal saline, and treat the subject with diphenhydramine 50 mg IV (or equivalent) and/or paracetamol 325 to 1000 mg (acetaminophen); remain at bedside and monitor patient until resolution of symptoms. Corticosteroid or bronchodilator therapy may also be administered as appropriate. If the infusion is interrupted, restart the infusion at 50% of the original infusion rate when symptoms resolve; if no further complications ensue after 30 minutes, the rate may be increased to 100% of the original infusion rate. Monitor the patient closely. If symptoms recur, re-administer diphenhydramine 50 mg IV, and monitor the patient until resolution of symptoms. The amount of study drug infused must be recorded on the CRF. If symptoms recur, treatment medications may need to be continued for 24-48 hours, and no further nivolumab will be administered at that visit.

The following prophylactic medications are recommended for future infusions:

- Diphenhydramine 50 mg (or equivalent),
- Paracetamol 325-1000 mg (acetaminophen) at least 30 minutes before additional nivolumab administrations, and
- Corticosteroids (recommended dose: up to 25 mg of IV hydrocortisone or equivalent) may be used, if necessary.

6.9.3 Grade 3 or 4 symptoms: Prolonged reaction (*i.e.*, not rapidly responsive to symptomatic medication and/or brief interruption of infusion); hospitalization indicated for other clinical sequelae (e.g., renal impairment, pulmonary infiltrates, etc.); life threatening; pressor or ventilatory support indicated.

- Immediately discontinue nivolumab infusion.
- Begin an IV infusion of saline and bronchodilators
- Epinephrine 0.2-1 mg diluted 1:1,000 for subcutaneous administration, or 0.1-0.25 mg diluted 1:10,000 for IV administration,

- Diphenhydramine 50 mg IV with methylprednisolone 100 mg IV (or equivalent), as needed.

Patient should be monitored until the investigator is comfortable that the symptoms will not recur. Nivolumab should be discontinued permanently.

Investigators should follow their institutional guidelines for the treatment of anaphylaxis. Monitor the patient until recovery from symptoms.

In the case of late-occurring hypersensitivity symptoms (*e.g.*, appearance of a localized or generalized pruritis within 1 week after treatment), symptomatic treatment may be given (*e.g.*, oral antihistamine, or corticosteroids). Additional treatment prior to next dose may be given according to the guidelines above.

Note: late occurring events including isolated fever and fatigue may represent the presence of systemic inflammation.

7. DOSING DELAYS/DOSE MODIFICATIONS

Note: If a patient experiences several AEs and there are conflicting recommendations, the investigator should use the recommended treatment modification for the most severe AE.

7.1 Nivolumab and Ipilimumab Dose Modifications

Below are dose modification tables for nivolumab and combination nivolumab with ipilimumab for the following adverse events. Please use as written and contact the drug monitor for any proposed changes.

Please refer to Appendix B, the Nivolumab Investigator's Brochure, or the Ipilimumab Investigator's Brochure for toxicity management algorithms which include specific treatment guidelines. These algorithms should be followed unless there are specific clinical circumstances for which the treating physician decides an alternative treatment approach is clinically appropriate. Consultation with the study PI or drug monitor is recommended.

In several places there are differences from the algorithms regarding protocol directed drug modifications and these are identified with (#). In these cases, please follow the protocol-specific guidelines in this section.

Generally, early evaluation while withholding drug, and appropriate treatment as indicated in the management tables and event specific guidelines is strongly encouraged.

- Any patient with grade 2 drug-related uveitis, eye pain, or blurred vision that does not respond to topical therapy and does not improve to grade 1 severity within the re-treatment period OR that requires systemic treatment should go off protocol therapy
- Patients with any AE, laboratory abnormality, or intercurrent illness which, in the judgment of the investigator, presents a substantial clinical risk to the patient with continued study drug dosing should go off protocol therapy.
- Any grade 3 or 4 drug-related laboratory abnormality or electrolyte abnormality that can be managed independently from underlying organ pathology with electrolyte replacement, hormone replacement, or insulin therapy, or that does not require treatment **does not** require discontinuation of protocol therapy.
- If any kidney-related AEs (e.g. elevated serum creatine levels, development of DSA or non-HLA antibodies, or development of severe proteinuria [>1 g/day]) are observed, nivolumab should be held, a renal allograft biopsy should be obtained, and treatment for allograft rejection should be started immediately (see Section 7.2).

Skin Rash and Oral Lesions	Management/Next Dose for Nivolumab and Combination Nivolumab/Ipilimumab
≤ Grade 1	No change in dose*
Grade 2	Hold* until ≤ grade 1 (#). Resume at same dose level.
Grade 3	Hold* until ≤ grade 1. Resume at same level at investigator's discretion
Grade 4	Off protocol therapy
*Patients with purpuric or bullous lesions must be evaluated for vasculitis, Steven-Johnson syndrome, TEN, and autoimmune bullous disease including oral lesions of bullous pemphigus/pemphagoid. Pruritus may occur with or without skin rash and should be treated symptomatically if there is no associated liver or GI toxicity. Note skin rash typically occurs early and may be followed by additional events particularly during steroids tapering.	
Recommended management: See Skin AE management guidelines.	

Liver Function AST, ALT, Bilirubin	Management/Next Dose for Nivolumab and Combination Nivolumab/Ipilimumab
≤ Grade 1	Hold, at investigator's discretion, until values return to ULN or baseline (#). Resume at same dose level.
Grade 2 (3 – 5 × ULN)	Hold until values return to baseline. Resume at same dose level.
Grade 3 (5 – 20 × ULN)	Hold until grade 1 (ULN – 3 x ULN) or baseline. Resume at same dose level, at investigator's discretion. If persistent (>7 days) or requires steroids, patients should go off protocol therapy
Grade 4	Off protocol therapy
Continued treatment of active immune mediated hepatitis may exacerbate ongoing inflammation. Holding drug to evaluate LFT changes and early treatment are recommended. LFT changes may occur during steroid tapers from other events and may occur together with other GI events including cholecystitis/pancreatitis.	
Note: Grades for liver function follow multiples of ULN, rather than multiples of baseline.	
Recommended management: See Hepatic AE Management Algorithm.	

Diarrhea/Colitis	Management/Next Dose for Nivolumab and Combination Nivolumab/Ipilimumab
≤ Grade 1	Hold until baseline (#). No change in dose.
Grade 2	Hold until baseline. No change in dose.
Grade 3	Resume at same dose level, at investigator discretion, if resolved within 7 days without steroids and with no evidence of colitis. If persistent (>7 days), or requires steroids, patients should go off protocol therapy.
Grade 4	Off protocol therapy
See GI AE Algorithm for management of symptomatic colitis. Patients with Grade 2 symptoms but normal colonoscopy and biopsies may be retreated after resolution. Patients who require systemic steroids should be taken off study treatment. If possible without compromising acute care, evaluate pituitary function prior to starting steroids. Evaluation for all patients for additional causes includes C. diff , acute and self-limited infectious and foodborne illness, ischemic bowel, diverticulitis, and IBD.	
Recommended management: See GI AE Management Algorithm.	

Pancreatitis Amylase/Lipase	Management/Next Dose for Nivolumab and Combination Nivolumab/Ipilimumab
≤ Grade 1	Continue at same dose level, if asymptomatic, at investigator's discretion.
Grade 2	Continue at same dose level, if asymptomatic, at investigator's discretion. If symptomatic, resume at same dose level once resolved.
Grade 3	Continue at same dose level, if asymptomatic, at investigator's discretion. Patients should have imaging done when clinically indicated (i.e. , grade 3 pancreatitis) before resuming treatment. Patients who develop symptomatic pancreatitis or diabetes mellitus should go off protocol therapy.
Grade 4	Hold until grade 2. Resume at same dose level if asymptomatic. Patients should have imaging done before resuming treatment, and when clinically indicated. Patients who develop symptomatic pancreatitis or diabetes mellitus should go off protocol therapy.
Patients may develop symptomatic and radiologic evidence of pancreatitis as well as DM and diabetic ketoacidosis (DKA). Lipase elevation may occur during the period of steroid withdrawal and with other immune mediated events or associated with colitis, hepatitis, and patients who have asymptomatic lipase elevation typically have self-limited course and may be re-treated. For treatment management of symptomatic pancreatitis please follow the Hepatic AE Management Algorithm.	

Pneumonitis	Management/Next Dose for Nivolumab and Combination Nivolumab/Ipilimumab
≤ Grade 1	Hold dose pending evaluation and resolution to baseline including baseline O2 saturation. Resume with no change in dose after pulmonary and/or infectious disease consultation excludes lymphocytic pneumonitis.
Grade 2	Hold dose pending evaluation. Resume with no change in dose after pulmonary and/or infectious disease consultation excludes ipilimumab and associated lymphocytic pneumonitis as the cause of the pneumonitis. Patients should go off protocol therapy if steroids are required.
Grade 3	Hold dose pending evaluation. Resume with no change in dose after pulmonary and/or infectious disease consultation excludes ipilimumab and associated lymphocytic pneumonitis as the cause of the pneumonitis. Patients should go off protocol therapy if steroids are required.
Grade 4	Off protocol therapy.
Distinguishing inflammatory pneumonitis is often a diagnosis of exclusion for patients who do not respond to antibiotics and have no causal organism identified including influenza. Most patients with respiratory failure or hypoxia will be treated with steroids. Bronchoscopy may be required and analysis of lavage fluid for lymphocytic predominance may be helpful. Patients with new lung nodules should be evaluated for sarcoid-like granuloma. Seasonal influenza killed vaccine should be recommended for all patients.	
Recommended management: See Pulmonary AE Management Algorithm.	

Other GI / Nausea and Vomiting	Management/Next Dose for Nivolumab and Combination Nivolumab/Ipilimumab
≤ Grade 1	No change in dose.
Grade 2	Hold pending evaluation for gastritis, duodenitis, and other immune AEs or other causes. Resume at same dose level after resolution to ≤ grade 1.
Grade 3	Hold pending evaluation until ≤ grade 1. Resume at same dose level. If symptoms do not resolve within 7 days with symptomatic treatment, patients should go off protocol therapy.
Grade 4	Off protocol therapy.
Patients with Grade 2 or 3 nausea or vomiting should be evaluated for upper GI inflammation and other immune related events.	

Fatigue	Management/Next Dose for Nivolumab and Combination Nivolumab/Ipilimumab
≤ Grade 1	No change in dose.
Grade 2	No change in dose.
Grade 3	Hold until ≤ grade 2. Resume at same dose level.
Grade 4	Off protocol therapy.
Fatigue is the most common adverse event associated with immune checkpoint therapy. Grade 2 or greater fatigue should be evaluated for associated or underlying organ involvement including pituitary, thyroid, or hepatic; or muscle inflammation (as assessed by creatine phosphokinase levels).	

Neurologic Events	Management/Next Dose for Nivolumab and Combination Nivolumab/Ipilimumab
≤ Grade 1	Hold dose pending evaluation and observation. Resume with no change in dose when resolved to baseline.
Grade 2	Hold dose pending evaluation and observation. Hold until ≤ grade 1. Patients should go off protocol therapy if treatment with steroids is required. Resume at same dose level for peripheral isolated nerve VII (Bell's palsy).
Grade 3	Off protocol therapy.
Grade 4	Off protocol therapy.
Patients with any CNS events including aseptic meningitis, encephalitis, symptomatic hypophysitis, or myopathy, peripheral demyelinating neuropathy, cranial neuropathy (other than peripheral nerve VII), GB syndrome, or myasthenia gravis should be off study.	
Recommended management: See Neurologic AE Management Algorithm.	

Endocrine Hypophysitis/Adrenal Insufficiency	Management/Next Dose for Nivolumab and Combination Nivolumab/Ipilimumab
≤ Grade 1	Hold pending evaluation, including consultation with an endocrinologist for evidence of adrenal insufficiency or hypophysitis. Patients with asymptomatic TSH elevation may continue treatment while evaluating the need for thyroid replacement.
Grade 2	Hold until patients are on a stable hormone replacement regimen. If treated with steroids, patients must be stable off steroids for 2 weeks. Resume at same dose level.
Grade 3	Hold until patients are on a stable replacement hormone regimen. If treated with steroids, patients must be stable off steroids for 2 weeks. Resume at same dose level.
Grade 4	Off protocol therapy.

Note: All patients with symptomatic pituitary enlargement, exclusive of hormone deficiency, but including severe headache or enlarged pituitary on MRI should be considered grade 3 events. Isolated thyroid or testosterone deficiency may be treated as grade 2 if there are no other associated deficiencies and adrenal function is monitored.
 
Pituitary function should be evaluated before beginning steroid therapy or replacement therapy of any kind.
 
*Note patients with thyroiditis may be retreated on hormone replacement therapy. Patients must be evaluated to rule out pituitary disease prior to initiating hormone replacement therapy.
 
Recommended management: See Endocrine AE Management Algorithm
	

Renal	Management/Next Dose for Nivolumab and Combination Nivolumab/Ipilimumab
≤ Grade 1	See Section 7.2
Grade 2	See Section 7.2
Grade 3	See Section 7.2
Grade 4	See Section 7.2

Infusion Reaction	Management/Next Dose for Nivolumab and Combination Nivolumab/Ipilimumab
≤ Grade 1	See Section 6.9
Grade 2	See Section 6.9
Grade 3	See Section 6.9
Grade 4	See Section 6.9

Fever	Management/Next Dose for Nivolumab and Combination Nivolumab/Ipilimumab
≤ Grade 1	Evaluate and continue at same dose level.
Grade 2	Hold until ≤ grade 1. Resume at same dose level.
Grade 3	Hold until ≤ grade 1. Resume at same dose level.
Grade 4	Off protocol therapy.
Patients with fever should be evaluated as clinically appropriate. Patients may experience isolated fever during infusion reactions or up to several days after infusion. Evaluation over the course of 1-2 weeks should be done for other autoimmune events that may present as fever.	

Cardiac*	Management/Next Dose for Nivolumab and Combination Nivolumab/ Ipilimumab
≤ Grade 1	Hold dose pending evaluation and observation.** Evaluate for signs and symptoms of congestive heart failure, ischemia, arrhythmia, or myositis. Obtain history, EKG, and CK (for concomitant myositis) and CK-MB tests. Repeat troponin and CK tests, and EKG every 2-3 days. If troponin and labs normalize without evidence of myocarditis, the patient may resume therapy. If labs worsen or symptoms develop then treat as below.
≥ Grade 2 with suspected myocarditis	Hold dose.** Admit to hospital and consult with a cardiologist. Rule out MI and other causes of cardiac disease, and begin cardiac monitoring. Obtain an echocardiogram and consider cardiac MRI and cardiac biopsy. Initiate high dose methylprednisolone and immune suppression as clinically indicated. If no improvement is seen within 24 hours consider adding either infliximab, ATG, or tacrolimus. Patients may resume therapy if there is a return to baseline and myocarditis is excluded or considered unlikely.
≥ Grade 2 with confirmed myocarditis	Off protocol therapy. Admit to CCU (consider transfer to nearest Cardiac Transplant Unit). Treat as above. Consider high dose methylprednisolone Add ATG or tacrolimus if no improvement.

*Including congestive heart failure, LV systolic dysfunction, myocarditis, or elevated levels of phosphocreatine kinase and/or troponin.

**Patients with evidence of myositis without myocarditis may be treated according to “All Other Events,” below.

Given the heightened risk for cardiac AEs, troponin should be monitored with each dose of nivolumab for the first two months to detect any early evidence of myocarditis. Baseline troponin should be obtained on study, after tacrolimus adjustment. Evaluation of cardiac function, including troponin and CPK levels, EKGs, and echocardiograms as clinically indicated, is recommended for any patients with a history of congestive heart failure or who are at risk because of underlying cardiovascular disease or previous exposure to cardiotoxic drugs.

Note: The optimal treatment regimen for immune mediated myocarditis has not been established. Since this toxicity has caused patient deaths, an aggressive approach is recommended.

All Other Events	Management/Next Dose for Nivolumab and Combination Nivolumab/Ipilimumab
≤ Grade 1	No change in dose.
Grade 2	Hold until ≤ grade 1 or baseline (exceptions as noted below).
Grade 3	Hold until ≤ grade 1 or baseline and patient no longer on steroid treatment, if initiated (exceptions as noted below). Patients should go off protocol therapy for events with a high likelihood of morbidity or mortality with recurrent events.
Grade 4	Off protocol therapy.
Recommended management: As clinically indicated	

Patients requiring high-dose steroid treatment for autoimmune or inflammatory AEs should go off study treatment except for short courses of tapering steroids for infusion reactions, skin rash, or endocrine events.

Patients with grade 3 thyroiditis and skin rash may continue therapy as for grade 2 events with resolution and stable replacement treatment.

Patients with thyroiditis or hypopituitarism who are stable as above may be restarted with replacement hormones including thyroid hormone and physiologic doses of corticosteroids. Please note that hypophysitis with symptoms of headache, visual or neurologic changes, or radiologic evidence of pituitary enlargement and other CNS events such as aseptic meningitis or encephalitis should be considered grade 3 events.

Prior to starting corticosteroids or hormone replacement for any reason, appropriate endocrine testing, including cortisol, adrenocorticotrophic hormone (ACTH), TSH, and T4, must be obtained to document baseline.

Please note that in some cases the treatment algorithms recommend steroids if symptoms do not resolve in 7 days. However, this recommendation is not meant to delay steroid treatment at any time it is clinically indicated.

Patients may be dose-delayed for evaluation and restarted depending on results.

Any patient started on corticosteroids who is later determined to not require steroid treatment for an autoimmune AE may resume therapy after a 2-week observation period without further symptoms at the discretion of the study PI or Investigator.

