5.4.3 Kidney Biopsy

If a patient shows markers of allograft rejection (see Section 7.2), a biopsy of their renal allograft should be obtained immediately. Patients may refuse biopsy and still remain on study. The biopsy should be performed according to local institutional standards. In addition, one ~1 cm, ~18-gauge core needle research biopsy sample should be procured, if possible. The research core sample plus biopsy material leftover after standard-of-care analysis should be provided to the Johns Hopkins team for research purposes. After collection, specimens will be formalin-fixed and paraffin-embedded per standard institutional protocol. Thereafter, samples should be sent as follows:

One H&E stained slide AND one unstained slide from every FFPE block from the standard-of-care surgical pathology specimens, or FFPE blocks if either of the above is not available. In addition, the research core sample should be embedded in paraffin and sent to the Tumor Microenvironment Core at Johns Hopkins University (see Section 5.5, below).

All slides and FFPE blocks can be sent at ambient temperature. Please ensure that each slide is labeled with the surgical pathology case number as well as the part number and block designation (number and/or letter, *e.g.*, 1A, 2A) to ensure that each slide can be matched to a particular block as outlined in the gross description on the pathology report.

See Section 5.3.1 for additional labelling instructions.

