7.2 Prednisone and Tacrolimus Dose Modifications for Allograft Rejection

Given the potential for rejection due to the administration of nivolumab and ipilimumab in this study, patients should be monitored closely for signs of rejection.

Markers of allograft rejection may include the following:

- Unexplained $\geq 20\%$ increase in serum creatinine over baseline,
- Development of donor-specific antigen (DSA) or non-HLA antibodies,
- Development of severe proteinuria (>1 g/day),
- Persistent increase in dd-cfDNA.

Serum creatinine (included in the comprehensive metabolic panel) will be monitored according to the schedule outlined in the treatment calendars (Section 11).

Donor-specific and non-HLA antibodies should be checked as clinically indicated at the direction of the institution's transplant nephrologist. Patients should be encouraged to report possible symptoms of rejection, including elevated temperature, elevated blood pressure, graft tenderness, and blood in the urine. Although experimental in this setting, dd-cfDNA levels (see Section 2.5.3 and the Biomarker Plan, Section 5.6) may be useful to monitor for signs of rejection.

Dipstick urinalysis should be performed per the schedule outlined in the treatment calendars. If 2+ or greater, a urine protein/creatinine ratio (spot or 24-hour) should be assessed at the direction of the institution's transplant nephrologist.

If rejection is suspected based on the above analyses, the following interventions will be triggered:

1. Hold or discontinue nivolumab (and ipilimumab, if applicable)
2. Immediately biopsy the renal allograft
 - a. If cell-mediated rejection: Increase the tacrolimus dose (target trough level = 5-10 ng/mL) and administer 500 mg IV methylprednisolone daily for 3 days, with a prednisone taper thereafter. If no improvement, administer 5 mg/kg infliximab.
 - b. If antibody-mediated rejection: Increase the tacrolimus dose (target trough level = 5-10 ng/mL), perform plasmapheresis, and administer IV immunoglobulin (Ig) per institutional protocol plus 500 mg IV methylprednisolone daily for 3 days with a prednisone taper thereafter.

A patient who experiences clinical benefit from the above regimen and still has a functional kidney allograft may restart study therapy after re-screening and consultation with the PI if the patient:

- Experienced an objective response or SD on study therapy,
- Experiences progressive or recurrent disease after having been off study therapy, and

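### Read literally, the kidney bullet in Section 7.1 orders an allograft biopsy and immediate rejection treatment for any kidney-related adverse event, whereas Section 7.2 acts on suspected rejection and sets treatment by biopsy type

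*Combined protocol and SAP*

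**What the plan says.** The bullet in Section 7.1 opens "If any kidney-related AEs (e.g. elevated serum creatine levels, development of DSA or non-HLA antibodies, or development of severe proteinuria" (above 1 g/day; creatinine is evidently meant) and continues "nivolumab should be held, a renal allograft biopsy should be obtained, and treatment for allograft rejection should be started immediately (see Section 7.2".

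Section 7.2 lists four possible markers of rejection: an unexplained "increase in serum creatinine over baseline" of at least 20%, donor-specific or non-HLA antibodies, proteinuria above 1 g/day, and a persistent rise in dd-cfDNA. It then says "If rejection is suspected based on the above analyses, the following interventions will be triggered". Step 1 is "Hold or discontinue nivolumab (and ipilimumab, if applicable"). Step 2 is "Immediately biopsy the renal allograft", with two treatment branches beneath it. The first reads "If cell-mediated rejection: Increase the tacrolimus dose (target trough level = 5-10 ng/mL) and administer 500 mg IV methylprednisolone daily for 3 days". The second, for antibody-mediated rejection, adds plasmapheresis and IV immunoglobulin.

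Section 5.4.3 says "If a patient shows markers of allograft rejection (see Section 7.2), a biopsy of their renal allograft should be obtained immediately". Footnote Q of calendar 11.1 and footnote N of calendar 11.2 confine the allograft biopsy to suspected rejection. The renal algorithm in Appendix B asks the clinician to exclude non-inflammatory causes first and, if one is found, to treat it and carry on with immunotherapy.

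**The concern.** The same kidney event is covered by two instructions that differ in what sets them off and in what happens at once. In 7.1 the trigger is any kidney-related adverse event, and rejection treatment is to start immediately. In 7.2 the trigger is suspicion of rejection, and treatment waits for a biopsy type.

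At stake is an unnecessary invasive procedure on the transplanted kidney, and a steroid course of 500 mg × 3 days = 1,500 mg of methylprednisolone, in a patient whose graft is not being rejected. Sites could also manage the same event differently in a trial of at most 16 patients.

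**Working it through.** The plan states no figure on this point, so the check compares texts.

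**1. The instructions side by side.**

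| Place | Trigger | Immediate step | Rejection treatment |
|---|---|---|---|
| 7.1 kidney bullet | Any kidney-related event; creatinine unqualified | Treatment | At once; no dependence on the biopsy result |
| 7.2 | Suspected rejection; creatinine rise unexplained and ≥20% over baseline | Biopsy | Under one of two branches, by biopsy type |
| 5.4.3 | The 7.2 markers | Biopsy | Not addressed |
| Footnotes Q (11.1), N (11.2) | Biopsy only if rejection is suspected | Not stated | By rejection type (footnote C of each calendar) |
| Appendix B, renal | Exclude non-inflammatory causes first | Not shown (flowchart missing) | If cause is non-inflammatory, treat that cause |

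**2. Overlap of triggers.** Of the three examples in 7.1, two (antibodies; proteinuria above 1 g/day) match 7.2 markers. The third, creatinine, loses both qualifiers: *unexplained*, and the 20% rise over baseline. The bullet names three of the four 7.2 markers; dd-cfDNA is absent.

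**3. Events that meet 7.1 but no listed 7.2 marker.** These are an explained creatinine rise of any size, a creatinine rise below 20%, and any other kidney event without one of the four markers. Illustration with assumed values: baseline creatinine 1.2 mg/dL rises to 1.8 mg/dL with an identified cause such as dehydration. The 7.2 size threshold is 1.2 × 1.20 = 1.44 mg/dL and the rise is 1.8 / 1.2 = 1.50, or 50%. The size criterion is met, but the rise is explained, so the marker as worded is not. If the rise is recorded as an adverse event, 7.1 still asks for biopsy and treatment.

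**4. Timing.** Section 7.2 has two treatment branches, both conditional on biopsy type, and no regimen for the period before the result. A reader sent there by 7.1 to treat immediately finds nothing to apply until the biopsy is read.

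**5. Does other text settle it?** The note opening Section 7 tells investigators which rule to follow when several adverse events conflict; it does not address two rules for one event. Section 7.1 says departures from the Appendix B algorithms carry a (#); the kidney bullet has none. The bullet does cite 7.2, and the renal table in 7.1 sends every grade to 7.2. That shows probable intent, but the words *any* and *immediately* still stand.

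**6. Effect on the analysis.** Section 9.5 defines the rejection rate by the 7.2 markers, not by the 7.1 bullet. The Section 9.1.1 design was checked exactly: P(reject null) = Σ over x = 2 to 9 of b(x; 9, p) × P(Bin(7, p) ≥ max(0, 5 − x)). This gives 0.0743 at p = 0.15 (stated 0.074) and 0.815 at p = 0.40 (stated 0.8). Neither uses anything from 7.1.

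**The case against.** The strongest reply is that 7.2 is the operative instruction. The bullet ends by pointing to it, the renal table defers to it at all four grades, and hold, biopsy, treatment can be read as prompt progress through the 7.2 steps. The Appendix B algorithm, which 7.1 tells investigators to follow, would itself catch an innocent cause. This stands as to intent and keeps the point small. It does not make the bullet consistent with the text it cites.

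A second reply is that a wide trigger is prudent. In Table 1, six of the nine kidney recipients had rejection and five lost the graft (loss was not reported for one), and Section 2.5.3 hypothesises that earlier recognition may save grafts. This also stands, and it is why the fix keeps the hold for every kidney-related event and the immediate biopsy when rejection is suspected.

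Three stronger readings are tempting but unsupported:

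- A reader might infer that 7.1 would drive tacrolimus up in a patient with tacrolimus-related kidney injury. But 7.2 gives the 5-10 ng/mL target only after rejection is typed, Section 6.1.3 puts dose changes under the transplant nephrologist, and 7.2 closes by leaving them to standard of care. A trough already above the usual 2-5 ng/mL would lie within or above the rescue range.
- A reader might infer that ipilimumab is left running because the bullet names nivolumab alone. Section 7.2 holds both drugs, and Section 6.3 applies Section 7 to the combination.
- A reader might infer that 7.2 forbids action without a listed marker. Its list is introduced as what markers may include, so it is open and clinical suspicion counts.

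**Conclusion.** The inconsistency is real and minor. As worded, the 7.1 bullet asks for a biopsy and immediate rejection treatment in events where 7.2, 5.4.3, the calendar footnotes and Appendix B would not, or not yet. The footnotes conflict less sharply, since they contrast suspected rejection with reactions that spare the kidney.

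Harm requires a site to follow 7.1 literally over the section it cites. The documents give no rate of kidney events that meet 7.1 but not 7.2, so no frequency can be stated. The creatinine example rests on assumed values and shows only that the two rules can diverge. The Appendix B flowchart is not available, so only its opening instruction is relied on.

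A reader might go further and suppose that rejection counts or the primary result would be distorted. The documents do not support that: the rejection rate is tied to 7.2, and the design figures reproduce.

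**What to change.** Replace the 7.1 kidney bullet with:

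> For any kidney-related AE, hold nivolumab (and ipilimumab) pending evaluation; if rejection is suspected on the Section 7.2 markers or clinical judgment, biopsy the allograft immediately and treat per Section 7.2.

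This keeps the cautious hold and the immediate biopsy, and makes the trigger agree with 7.2, 5.4.3, the footnotes and Appendix B. Whether to treat empirically before the biopsy result, or when a patient refuses the biopsy as 5.4.3 allows, is left to the transplant nephrologist.

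The cost is one reworded bullet, with no new visits, tests, patients or analyses. The downside is that a few mild or explained creatinine rises would no longer trigger an automatic biopsy. The 20% rule, antibodies, proteinuria, dd-cfDNA and clinical judgment remain as safeguards.
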